3.2.3 Immunogenicity Endpoints (In Maternal and Infant Subjects as Stated)

- Serum immunoglobulin G (IgG) antibody concentrations specific for the F protein antigen measured by enzyme-linked immunosorbent assay (ELISA) and serum concentrations of antibodies competitive with palivizumab for binding to the RSV F

protein. Derived/calculated endpoints based on these data will include geometric mean concentrations as ELISA Units (GMEU) or μ g/mL as appropriate, geometric mean fold-rise (GMFR), proportion of subjects with \geq 2-fold and \geq 4-fold increases in concentration from baseline (seroconversion rate, SCR [maternal subjects only]), and seroresponse rate (SRR). Analyses will be used to evaluate:

- Immunogenicity through six months post-delivery in maternal subjects.
- Transplacental transfer of maternal antibodies specific for RSV described as a ratio of levels in maternal and cord blood at delivery.
- Infant RSV-specific antibody decay during the first six months of life relative to cord blood levels.
- Immune correlates of risk of RSV LRTI in infants based on anti-RSV F protein IgG or palivizumab-competitive antibody responses in the infant and/or cord blood, and maternal subjects at delivery.
- Serum microneutralization (MN) titers against RSV/A and B in maternal and infant subjects at select time-points may be generated for a subset of the population using the derived/calculated endpoints previously referenced, based on geometric mean titer (GMT). An external laboratory, whose personnel are blinded to study treatment, will perform RSV/A and B MN testing during study conduct and after Day 180 unblinding. Final MN results, because of their time-consuming nature, may be provided as one or more sequential addenda to the main study report.

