11.1. Analysis of the Secondary Objectives of Immunogenicity

The principal variables of interest for assessment of immune response to the RSV F vaccine will be anti-F IgG EU and PCA concentrations that will be determined at all prospectively defined time-points as stated below. Additional immunogenicity variables will be RSV/A and B MN titers, which will be measured at the baseline and delivery visits for maternal subjects and at the delivery and D+14, D+35, D+60, D+90, D+120, and D+180 visits for infant subjects. For the analysis of paired immunogenicity measures, geometric mean of fold rise in post-vaccination measures compared to baseline (pre-vaccination) in maternal subjects (GMFR) and geometric mean ratio (GMR) of paired samples over time within a maternal subject, an infant subject, or a maternal and infant subject pair (GMR) will be summarized. GMC, GMEU, GMT, and GMFR/GMR will be calculated as the antilog of the mean and 95% CI of \log_{10} -transformed values. The values reported as below the LLOQ of the assay will be set to half of LLOQ. In addition, seroconversion rates (SCR) based on ≥ 2 - and ≥ 4 -fold rise thresholds and seroresponse rates (SRR) will be calculated as defined below.

The following immunogenicity outcome measures and their 95% CI will be summarized by treatment group.

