11.1.1. Anti-F IgG ELISA (EU)

The following parameters will be analyzed for maternal subjects.

- GMEU at baseline (pre-vaccination on Day 0) and post-vaccination on Day 14, at delivery, and postpartum on Days 35 and 180 (as applicable).
- GMFR_{Post/Pre} on post-vaccination Day 14, at delivery, and postpartum on Days 35 and 180 (as applicable).
- GMR_{Cord/MS} on the within-maternal-infant pair for cord blood over maternal serum (MS) at delivery, e.g., GMFR Transplacental Transfer Proportion.
- Seroconversion Rate (SCR) – defined as the proportion of subjects with ≥ 2 -fold and ≥ 4 -fold increases in concentration from baseline, calculated as the proportion (%) of subjects in a particular treatment group with a baseline concentration $<$ LLOQ and a post-vaccination concentration $\geq 2 \times$ LLOQ and $\geq 4 \times$ LLOQ, respectively, or a baseline concentration \geq LLOQ and a ≥ 2 -fold and ≥ 4 -fold, respectively, increase in

post-vaccination concentrations. These response rates will be summarized post-vaccination on Day 14, at delivery, and postpartum on Days 35 and 180 (as applicable).

- Seroresponse rate (SRR) – defined as the proportion (%) of subjects in the RSV F treatment group with an increase in antibody level over a specific time period which is greater than the 95th percentile of antibody response in the absence of active vaccine based on the behavior of placebo recipients' sera over the same period. SRR will be analyzed by computing the ratio (post-vaccination/pre-vaccination [Day 0]) at each post-vaccination time-point on Day 14, at delivery, and postpartum on Days 35 and 180 (as applicable). At a given time-point, the 95th percentile of the ratios in the placebo group will be estimated. A subject in any treatment group will be identified as a responder if its ratio is greater than the estimated threshold in the placebo group at the given time-point.

The following parameters will be analyzed for infant subjects:

- GMEU of anti-F IgG in cord blood and on D+14, D+35, D+60, D+90, D+112, and D+180.
- GMR_{AD/Cord} of anti-F IgG EU within-subject ratios after delivery (AD) on D+14, D+35, D+60, D+90, D+120, and D+180 over cord blood value at delivery.

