11.1.4. Infants Antibody Decay Modeling

To estimate the decay of antibody levels in per protocol infants (PP-IMM-I) that result from RSV F protein vaccine immunization in pregnant women, the log10 transformed antibody

levels will be used as the independent variable and the actual age of infant subjects in days at the time of sample collection as the exploratory variable in the regression analysis. The estimated slope will be used to estimate the half-life as $\log_{10}(2)/\text{slope}$ with the corresponding 2-sided 95% confidence interval. All observed values, except for the measures reported as < LLOQ, for each time-point and infant cohort (Phlebotomy Cohort 1, Cohort 2, and Cohort 3) will be pooled to assess the persistence of anti-F IgG antibody, PCA, and/or MN levels over time. Since values reported as < LLOQ do not provide the exact time when the values crossed the LLOQ, they will be excluded from the half-life estimation. All measurements from subjects with at least two \geq LLOQ measures will be included in the analysis. A conventional first order antibody decay model will be used for analysis. A second order or other, more complex, antibody decay model may be further developed to explain the rate of decay of antibody levels in the infants in the study, albeit the dataset may not be sufficiently rich to support more complex models.

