16. DATA HANDLING CONVENTIONS

All statistical analyses will be 2-tailed and assessed at the 5% significance level.

All output will be incorporated into Microsoft Word (including rtf format) or Excel files, or Adobe Acrobat PDF files, sorted and labeled according to the International Conference on Harmonization (ICH) recommendations, and formatted to the appropriate page size(s).

Tabulations will be produced for appropriate demographic, baseline, and safety parameters. For categorical variables, summary tabulations of the number and percentage of subjects within each category (with a category for missing data) of the parameter will be presented. For continuous variables, the number of subjects, mean, median, standard deviation (SD), minimum, and maximum values will be presented.

For all analyses, a two-sided p-value of < 0.05 (one-sided p-value < 0.025 where appropriate) will be considered statistically significant except for the primary efficacy endpoint, medically significant RSV LRTI through 90 day that will be evaluated using a one-sided p value of 0.0124

All references to analysis of GMEU/GMC/ GMT will be interpreted as analysis of the log (base 10) of EU or concentration values or of the reciprocal titers (e.g., the reciprocal titer of 1:160 is the number 160). Values recorded as below the lower limit of quantitation (LLOQ) of the assay for PCA and anti-F IgG will be set to half LLOQ for the purposes of GMEU/GMC, and GMFR analyses. For MN assays, titers will be reported in International Unit (IU) with the LLOQs of 13 for RSV/A and 8 for RSV/B. Titers below the LLOQs will also be set to half LLOQ, 6.5 IU for RSV/A and 4 IU for RSV/B.

For all data analyses and summary tabulations, categories for analysis and presentation will consist of the RSV F vaccine treatment groups. All descriptive statistical analyses will be performed using SAS statistical software Version 9.3 or higher in a Windows environment, unless otherwise noted. Medical history and AEs will be coded using the MedDRA Version 16.1.

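### Half-LLOQ substitution lets the assay limit set part of the infant/cord and cord/maternal antibody ratios, and the SAP neither counts the affected pairs nor tests their effect

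*Protocol*

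**What the plan says.** Protocol 3.2.3 names two paired quantities: "Infant RSV-specific antibody decay during the first six months of life relative to cord blood levels" and "Transplacental transfer of maternal antibodies specific for RSV described as a ratio of levels in maternal and cord blood at delivery". Neither that section nor Protocol 10.5 says how values below the LLOQ enter them.

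The rule is in SAP 11.1. Geometric means and paired ratios are antilogs of mean log10 values, and "The values reported as below the LLOQ of the assay will be set to half of LLOQ". SAP 11.1.1 defines GMR AD/Cord from "within-subject ratios after delivery (AD) on D+14, D+35, D+60, D+90, D+120, and D+180 over cord blood value at delivery", and GMR Cord/MS as cord over maternal serum at delivery. SAP 11.1.2 and 11.1.3 carry these definitions to PCA and microneutralization (MN).

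SAP 16 repeats the rule for the ELISAs: "Values recorded as below the lower limit of quantitation (LLOQ) of the assay for PCA and anti-F IgG will be set to half LLOQ". That sentence names fold-rises but not GMR; SAP 11.1 covers both, and Protocol 10.5 labels both paired ratios GMFR. For MN, SAP 16 gives titers in IU "with the LLOQs of 13 for RSV/A and 8 for RSV/B" and adds: "Titers below the LLOQs will also be set to half LLOQ, 6.5 IU for RSV/A and 4 IU for RSV/B".

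The half-life model in SAP 11.1.4 follows a different rule: "Since values reported as < LLOQ do not provide the exact time when the values crossed the LLOQ, they will be excluded". It also requires at least two quantifiable values per infant.

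**The concern.** Half-LLOQ is an ordinary convention for a geometric mean at one time-point. In a within-pair ratio it does something else: the substituted value depends on the assay, not on the infant, so part of the ratio is set by the LLOQ. There are two separate mechanisms. Pairs below the LLOQ at both ends are uninformative but enter as 1.0. Pairs with quantifiable cord blood and an infant value below the LLOQ enter at a floor, however far antibody has fallen.

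Transfer and decay are stated secondary objectives, and the ratios are tabulated by arm. If placebo cord levels lie nearer the LLOQ than vaccine cord levels, the two arms can show different AD/Cord ratios with the same true decay. That ordering is likely, since the vaccine is meant to raise infant antibody, but it is an inference. The SAP does not ask for the number of affected pairs, so a reader of the tables could not tell how much of a ratio came from substitution.

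**Working it through.** **The plan's own figures.** MN substitutes: 13/2 = 6.5 IU (RSV/A) and 8/2 = 4 IU (RSV/B). Both agree with SAP 16.

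**Single pairs, RSV/A (LLOQ 13 IU).**
- Cord 10, infant 3: true ratio 0.30; scored 6.5/6.5 = 1.0.
- Cord 13, 26, 52 or 104, infant below LLOQ: scored 6.5/cord = 0.50, 0.25, 0.125 or 0.0625, whatever the true infant value.

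**Effect of both-below pairs on a group ratio.** With a share q of such pairs and a geometric mean ratio g in the rest, the reported GMR is g^(1−q).
- g = 0.10: 0.112, 0.126, 0.178 and 0.316 at q = 5%, 10%, 25% and 50%.
- Transfer ratio 1.20: 1.178, 1.147 and 1.095 at q = 10%, 25% and 50%.
- Transfer ratio 0.90: 0.910, 0.924 and 0.949 at the same q.

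**Both mechanisms together, AD/Cord.** The documents do not give the ELISA LLOQs, the share below them, the half-life or the spread. Assumptions: half-life 40 days; log10 SD 0.3 between infants and 0.1 within pairs. True ratios are 2^(−90/40) = 0.21 at D+90 and 2^(−180/40) = 0.044 at D+180. Simulated ratios under the SAP rule:

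| Cord GM / LLOQ | D+90 (true 0.21) | D+180 (true 0.044) |
|---|---|---|
| 1 | 0.55 | 0.54 |
| 3 | 0.23 | 0.17 |
| 10 | 0.20 | 0.057 |
| 30 | 0.21 | 0.041 |

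Hand check of the 0.54. At 1× and D+180 practically every infant value is below LLOQ. Half the cords are below LLOQ too and give a log10 ratio of 0. For the other half, cord averages 0.3 × √(2/π) = 0.239 above log10 LLOQ, so the log10 ratio is −0.301 − 0.239 = −0.540. The mean is −0.270, and 10^−0.270 = 0.54.

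**Cord/MS.** With 80% of mothers below LLOQ (assumed), the same SDs and the within-pair error in cord only, a true 1.15 is reported as 1.10 and a true 0.80 as 0.93.

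**Choice of remedy.** Put 0.1 log10 error in both members of the pair.
- Dropping pairs with a denominator below LLOQ and censoring the numerator gives Cord/MS 1.04 for a true 1.15 and 0.72 for 0.80. For 1.15 this is worse than half-LLOQ (1.08). Keeping only denominators above LLOQ favours those measured too high.
- A bivariate normal likelihood that keeps every pair and left-censors each value below LLOQ gives 1.16 and 0.80, and 0.21 for D+90 AD/Cord at 1× and 3× LLOQ. The 1× result leans heavily on normality: mean infant log10 is −0.677 relative to LLOQ and the SD is √(0.3² + 0.1²) = 0.316, so about 98% of infant values are censored.

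**The case against.** The strongest reply is that the size is unproven. The anti-F IgG and PCA LLOQs are not stated, Protocol 1.7 describes all adults as already primed to RSV, and the anti-F ELISA starts at dilutions of 1:10 (Protocol 7.2.1). If cord levels are about 30 times the LLOQ or more in both arms, the convention does no material harm. At D+90 the error is about 10% or less from 3× upward, and at 10× (D+90) and 30× (D+180) it runs slightly toward faster decay. All of this stands. It limits the claim to a conditional one, and it is also a reason to print the counts.

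Four stronger readings are tempting, and the documents do not support them.
- A reader might infer that vanished antibody is scored as fully persistent. A pair scoring 1.0 had no quantifiable cord antibody to lose. Antibody that was quantifiable and then fell below LLOQ scores at most 0.5, which is visible decay.
- A reader might convert 0.54 at D+180 into a half-life near 200 days. The SAP does not derive half-life from this ratio; SAP 11.1.4 estimates it separately. That model does not repair the ratio, which is its own output, and its exclusion rule has its own bias: under another set of assumptions (ln-scale SDs 0.8 and 0.2), a true 30 days is estimated as about 49 at 2× LLOQ.
- A reader might infer that the interval is too narrow because pairs fixed at 1.0 add no variance. At 1× and D+180 the log10-ratio SD under substitution was 0.30 against a true 0.10, so the direction is not established.
- A reader might call the difference between arms an artefact. No between-arm test of these ratios is planned, and geometric means at each infant time-point are also reported, which may show an arm nearing the assay floor.

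**Conclusion.** The concern holds as a conditional weakness in a descriptive secondary analysis. It is certain from the text that both ratios use half-LLOQ substitutes, that both-below pairs score exactly 1.0, that infant values below the LLOQ are floored relative to cord, and that the current SAP plans neither a count of these pairs nor a sensitivity analysis for them. Materiality is not established. Under the stated assumptions the D+180 ratio is overstated about twelvefold at 1× LLOQ (0.54/0.044), about fourfold at 3× (0.17/0.044) and by about 30% at 10× (0.057/0.044); at 30× it is slightly understated. Cord/MS moves toward 1.0 from either side, so no claim of persistence applies to it. A spurious difference between arms requires placebo levels nearer the LLOQ, which is likely but inferred. The change is worth making because it is cheap and because the rule as written can yield a wrong ratio without any sign of it in the table.

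**What to change.** In SAP 11.1 and 16:

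1. Keep the half-LLOQ GMR as the tabulated convention.
2. For each assay, arm and time-point, print the number and percent of pairs with the numerator below, the denominator below, and both below the LLOQ.
3. Add a sensitivity analysis for GMR AD/Cord and GMR Cord/MS: a bivariate normal likelihood for the paired log10 values, each value below the LLOQ left-censored, and no pair dropped.
4. Do not exclude pairs because the denominator is low; that selects on measurement error.
5. State a percent censored above which a cell is flagged as not estimable.
6. Where the two analyses disagree, interpret the by-arm ratios from the censored one.

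The cost is SAP wording and a short extra program on data already collected. The price in interpretation is a normality assumption, which carries more weight as censoring rises, and some late placebo cells that may become not estimable.

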3.2.4 Safety Endpoints

3.2.4.1 In All Infant Subjects

- Percentages of term (\geq 37 weeks gestational age), healthy infants appropriate for gestational age (as determined by ultrasound gestational age assessment), APGAR scores, length, birth weight, frontal-occipital head circumference (FOC), and physical examination at birth.
- Percentages of infants with AEs and SAEs (with special attention to congenital anomalies; respiratory failure other than RSV-associated hospitalization; neonatal death; infant death; sudden infant death syndrome; asphyxia; neonatal or hypoxic-ischemic encephalopathy; or other adverse events or complications of adverse events that necessitate hospitalization) during the neonatal period and through the first year of life.
- Percentages of infants with unsolicited adverse events (including abnormalities detected in routine metabolic screening blood and neonatal hearing tests), unscheduled medical visits for adverse events, and serious adverse events through the first year of life.
- Percentages of infants with developmental delay, as measured by the outcome of testing using a validated developmental scale at six months and at one year, in infants of RSV F vaccinees as compared to placebo.

3.2.4.2 In Maternal Subjects

- Percentages of subjects with solicited injection site and systemic reactogenicity within seven days of vaccination.
- Percentages of subjects with unsolicited (local and systemic) adverse events (AEs), unscheduled medically-attended adverse events (MAEs), significant new medical conditions (SNMCs), and serious adverse events (SAEs) through delivery and six (6) months thereafter.
- Clinical safety laboratory assessments of select serum chemistry and hematology parameters through delivery.
- Percentages of subjects with Caesarean, vaginal, or instrument-assisted vaginal modes of delivery.
- Percentages of subjects with post-immunization onset of specific complications of third-trimester pregnancy and delivery including:
 - Pregnancy complications:
 - Stillbirth,
 - Preterm birth (moderate to late preterm: 32 to < 37 weeks of gestation; very preterm: 28 to < 32 weeks of gestation),
 - Preterm premature rupture of membranes,
 - Placental abruption,
 - Hypertensive disorders of pregnancy including: gestational hypertension, pre-eclampsia/eclampsia,
 - Third-trimester hemorrhage, and
 - Gestational diabetes.
 - Labor and delivery complications:
 - Emergency Caesarean (C)-section for maternal or fetal indications,
 - Postpartum hemorrhage,
 - Chorioamnionitis, and
 - Maternal fever or infection.

3.2.5 Exploratory Endpoints (In Maternal and Infant Subjects as Stated)

- Percentages of infants with medically-significant RSV LRTI from delivery through 90, 120, 150 and 180 days of life defined as per the primary efficacy endpoint with the exception that evidence of RSV infection, LRTI, hypoxemia, and/or tachypnea may be based on either or both of the observations of the clinical site staff using sponsor-supplied devices and diagnostic tests OR review and abstraction of medical records for infants undergoing hospitalization for a respiratory serious adverse event.
- Percentages of infants with RSV LRTI with EITHER severe hypoxemia ($\text{SpO}_2 < 92\%$ at sea level or < 87% at altitudes > 1800 meters) OR the documented use of oxygen by high flow nasal cannula OR continuous positive airway pressure (CPAP) OR bilevel positive airway pressure (BiPAP) OR Bubble CPAP OR bag-mask ventilation OR

intubation with subsequent mechanical (or manual) ventilation OR extracorporeal membrane oxygenation (ECMO) from delivery through 90, 120, 150, and 180 days of life defined as per the corresponding secondary efficacy endpoint with the exception that evidence of RSV infection, LRTI, severe hypoxemia, and/or respiratory support may be based on either or both of the observations of the clinical site staff using sponsor-supplied devices and diagnostic tests OR review and abstraction of medical records for infants undergoing hospitalization for a respiratory serious adverse event.

- Percentages of infants with RSV LRTI requiring hospitalization from delivery through 90, 120, 150, and 180 days of life defined as per the corresponding secondary efficacy endpoint with the exception that evidence of RSV infection and LRTI may be based on either or both of the observations of the clinical site staff using sponsor-supplied devices and diagnostic tests OR review and abstraction of medical records for infants undergoing hospitalization for a respiratory serious adverse event.
- Percentages of infants with RSV LRTI associated with EITHER hypoxemia (peripheral oxygen saturation [SpO_2] < 95% at sea level or < 92% at altitudes > 1800 meters) OR tachypnea (≥ 60 bpm for infants 0 to 59 days of age or ≥ 50 bpm for infants ≥ 60 days of age [WHO Handbook, Integrated Management of Childhood Illness criteria for tachypnea]) from delivery through 90, 120, 150, and 180 days of life. Data concerning documentation of RSV infection, LRTI symptoms and signs, hypoxemia and/or tachypnea may be obtained from the observations of the clinical site staff OR review and abstraction of medical records for infants undergoing hospitalization for a respiratory serious adverse event.
- Percentages of infants with RSV LRTI resulting in death from delivery through 90, 120, 150, and 180 days of life. Evidence of RSV infection and LRTI may be based on either or both of the observations of the clinical site staff using sponsor-supplied devices and diagnostic tests OR review and abstraction of medical records for infants undergoing hospitalization for a respiratory serious adverse event.
- Percentages of infants with RSV LRTI (all severities) from delivery through 90, 120, 150, and 180 days of life. Evidence of RSV infection and LRTI may be based on either or both of the observations of the clinical site staff using sponsor-supplied devices and diagnostic tests OR review and abstraction of medical records for infants undergoing hospitalization for a respiratory serious adverse event.
- Counts and incidence rates of infant healthcare interventions associated with wheezing through the first year of life.
- Percentages of maternal subjects with RSV-related respiratory illness as observed by the clinical study staff and detected by active and passive surveillance from vaccination through six months after delivery, overall and by pathogen(s).
- Percentages of infant subjects with all-cause LRTI, with or without tachypnea, hypoxemia, or severe hypoxemia, as detected by active and passive surveillance from vaccination through six months after delivery, overall and by pathogen(s).
- Percentages of infant and maternal subjects with non-RSV respiratory viruses, overall and by pathogen(s), through six months after delivery.

A Clinical Endpoint Adjudication Committee (CEAC) composed of expert pediatricians (see Section 10.4.2) will carry out a blinded review of all potential exploratory endpoint cases involving RSV LRTI in infants to determine if they fulfill the relevant endpoint criteria in a temporally plausible relationship consistent with RSV disease as observed in clinical practice. Only CEAC-confirmed cases will be used for exploratory endpoints.

